**Which Committee will review this protocol?**

The Clinical Research Committee - (CRC)

## Protocol Body

### 1.0 Objectives

#### 1.1 Primary Objective:

- 1.1.1 To determine the incidence of secondary graft failure with brentuximab maintenance post allogeneic or haploidentical stem cell transplant.

#### 1.2 Secondary Objectives:

- 1.2.1 To evaluate the hematologic toxicity of brentuximab maintenance after an allogeneic stem cell transplant.
- 1.2.1 To determine the response rates in patients who start post transplant brentuximab with measurable disease.
- 1.2.2 To determine the relapse rate in this patient population
- 1.2.3 To determine the incidence of cytomegalovirus (CMV) reactivation and/or CMV disease.
- 1.2.4 To determine the incidence of acute graft-versus-host disease (GVHD).
- 1.2.5 To describe the effect of brentuximab on central and effector memory and naïve CD4 and CD8 cell subpopulations.
- 1.2.6 To describe the effect of brentuximab on serum CD30 levels both in patient subsets with and without GVHD.
- 1.2.7 To determine the progression free survival and overall survival of patients on brentuximab maintenance.

### 2.0 Background

#### 2.1 Allogeneic hematopoietic stem cell transplants for Hodgkin lymphoma:

Hodgkin's lymphoma (HL) is primarily treated with conventional chemotherapy to which it is highly responsive(1). After relapse the standard of care is an autologous stem cell transplant (SCT) (2). The results of auto SCT are variable with recurrence of HL ensuing in 50% of patients after autologous SCT(3). Prognosis of patients who relapse following an auto SCT is generally poor, although allogeneic SCT can induce long-term remissions through a graft-vs.-lymphoma (GVL) effect. The use of myeloablative regimens for allogeneic SCT results in prohibitively high treatment related mortality (TRM), upward of 22% in the first 100 days(4). Reduced intensity conditioning (RIC) treatments have been shown to significantly reduce TRM, although relapse remains a significant problem. Anderlini and colleagues at our institution (5) have demonstrated decreased TRM using fludarabine/melphalan as conditioning with rates of TRM of 7% at day 100 and 15% at 2 years. Their data reveals an overall survival (OS) rate of 64% and progression free survival (PFS) of 32% at 2 years, with a 2-year rate of disease progression or relapse at 55%. In an EBMT analysis of 250 patients who received a reduced intensity allo SCT for found that chemorefractory disease was associated with PFS and OS of 8% and 25% respectively at 2 years. Patients in CR at time of transplant PFS had a 3-year PFS of 42%(6). Sureda et al.(3) reported on RIC allo SCT using fludarabine and melphalan and observed a TRM of 8% at 100 days and 15% at 1 year. The estimated PFS for the entire allografted population was 24% at 4 years and patients allografted in CR had PFS of 50% at 4 years. Alvarez et al.(8) found that patients allografted with chemosensitive disease (including CR patients) at time of transplantation had a PFS at 2 years of

55%  $\pm$  16%. These studies illuminate that although patients in CR and with chemosensitive disease have better outcomes, disease progression is still in the range of 50% 2-4 years post transplant. Reduced intensity allogeneic transplant can lead to long term disease free survival, however relapse after allo SCT has very poor outcomes with less than 50% of patients surviving past 3 years(7). Beyond allogeneic transplant there are limited effective therapeutic options.

This is an extremely high risk patient population for progression of disease and brentuximab vedotin has been shown to induce partial and complete responses in patients who relapse post allogeneic transplant with acceptable toxicity.(7) Decreasing the relapse rate will be a substantial factor in improving overall survival for these patients, which is the rationale for using brentuximab vedotin as a maintenance therapy early post-allogeneic transplant.

## **2.2 Allogeneic hematopoietic stem cell transplantation in anaplastic large cell lymphoma:**

Systemic anaplastic large cell lymphoma (ALCL) is a rare, mature T-cell non-Hodgkin lymphoma (NHL). This disease accounts for approximately 3% of adult NHLs, 10-15% of pediatric NHLs and 25% of newly diagnosed peripheral T cell lymphomas in North America(9). ALCLs that do not express anaplastic lymphoma kinase (ALK) have a particularly poor prognosis with fewer than 30% of patients achieving long term disease free survival(10). Patients with relapsed or refractory disease are considered incurable with chemotherapy alone, and often proceed to high dose chemotherapy followed by autologous transplant or allogeneic SCT. Allogeneic transplant may benefit a subset of patients who relapse if they have a good performance status and matched related or unrelated donors. Corradini et al. (10) reported on a phase II study of RIC allogeneic stem cell transplantation in 17 patients with relapsed or refractory peripheral T-cell lymphoma (PTCL) and after a median follow-up time of 28 months, the estimated 3-year OS and PFS rates were 81% and 64%, respectively. The TRM at 2 years was considered acceptable at only 6%. Two of 13 patients in CR relapsed after transplant while overall 3 of the total 17 patients had progressive disease.

## **2.3 Haploidentical hematopoietic stem cell transplantation in Hodgkin Lymphoma:**

One of the limitations with an allogeneic stem cell transplant is that the majority of patients lack an identical sibling and no more than 50% of patients, searching the Registries for unrelated donors or cord blood units, undergo an allo-SCT (World Marrow Donor Association data, 2012 unpublished). Recently, encouraging results have been obtained with HLA haploidentical-related donor, following an NMA regimen, unfractionated BM and post-transplantation CY (PT-CY) (11).

Twenty-six patients with advanced Hodgkin's disease received a related HLA haploidentical unmanipulated BMT, following a non-myeloablative conditioning with low-dose TBI and GVHD prophylaxis consisted of high-dose post-transplantation CY (PT-CY), mycophenolate and a calcineurin inhibitor. The incidence of grade II-IV acute GVHD and of chronic GVHD was 24% and 8%, respectively. With a median follow-up of 24 months (range 18-44) 21 patients are alive, 20 disease free. The cumulative incidence of TRM and relapse was 4% and 31%, respectively. The actuarial 3-year survival is 77%, the actuarial 3-year PFS is 63%. (12).

Haploidentical transplant has been tested by multiple centers for Hodgkin lymphoma and found to preserve graft versus lymphoma effect without significant additive toxicity.

## **2.4 CD30 Expression:**

Hodgkin Reed-Sternberg cells express the CD30 antigen almost universally (11). Systemic ALCL tumors present with large blastic CD30-expressing cells and the CD30 antigen is also expressed in some cutaneous T-cell lymphomas (CTCLs), other natural killer (NK) and T-cell neoplasms, a subset of B-cell lymphomas and embryonal carcinoma.(13,14) CD30 is a transmembrane glycoprotein receptor member of the tumor necrosis factor (TNF) receptor superfamily 8 (TNFRSF8). The functions of CD30 are not fully understood. Its distribution on normal cells is restricted to activated T and B cells and macrophages(12,15), and it seems to be an activator of the canonical and alternative nuclear factor- $\kappa$ B (NF- $\kappa$ B) pathways, transducing a cell survival signal. (6, 16,18)

Brentuximab vedotin is a CD30-directed antibody-drug conjugate consisting of 3 components: the monoclonal chimeric antibody cAC10 that is specific for human CD30 the potent antimicrotubule agent monomethyl auristatin E (MMAE) a protease-cleavable linker that covalently attaches MMAE to cAC10. The biologic activity of brentuximab vedotin results from a multi-step process. Binding of the antibody-drug conjugate (ADC) to CD30 on the cell surface commences internalization of the ADC-CD30 complex, which then traffics to the lysosomal compartment where MMAE is released via proteolytic cleavage. Binding of MMAE to tubulin disrupts the microtubule network within the cell, induces the mitotic spindle cell cycle checkpoint and results in growth arrest and apoptotic death of the CD30-expressing tumor cells. (16)

Younes and colleagues reported the initial data in a phase I dose escalation trial that enrolled 45 patients with relapsed or refractory CD30+ hematologic malignancies. They showed 20 objective responses, including 11 complete remissions (CRs), in 17 patients and tumor regression was observed in 86% of evaluable patients. Seventy-three percent of patients in that trial had undergone autoSCT.(19) Subsequently this group presented a phase 2 study using Brentuximab vedotin (1.8 mg/kg intravenously every 3 weeks) after auto SCT for 102 patients with relapsed/refractory CD30+ HL and revealed objective responses in 75% of patients, with CRs observed in 34% of patients.(20) The estimated 12-month survival was 89% and the median PFS was 5.6 months. Adverse events associated with brentuximab vedotin were typically grade 1 or 2 and able to be managed through standard supportive care. Cumulative peripheral neuropathy, the most clinically meaningful adverse event, improved or resolved completely in 80% of patients during the study. Patients who had previously received an alloSCT were excluded from both of these trials.

Pro et al.(18), demonstrated an objective response of 86% and complete remission of 57% in 58 patients with relapsed or refractory systemic anaplastic large cell lymphoma (ALCL) treated at the dose of 1.8 mg/kg every 3 weeks. The median durations of overall response and CR were 12.6 and 13.2 months, respectively. Grade 3 or 4 adverse events in >10% of patients were neutropenia (21%), thrombocytopenia (14%), and peripheral sensory neuropathy (12%).

## **2.5 Transplantation and use of Brentuximab Vedotin:**

More recently Gopal et al.,(7) published their experience with 25 HL patients treated with brentuximab at 1.8 mg/kg every 21 days after relapse post allogeneic SCT. Overall and complete response rates were 50% and 38% respectively, median OS not reached. In their study, the drug was very well tolerated with most common grade >/-3 side effects being: neutropenia (24%), anemia (20%), hyperglycemia (12%) of which all were reversible. CMV was detected in 5 patients and was clinically significant in 1 patient. Sixteen patients (64%) had an objective response after allo SCT, including 14 CRs and 2 PRs. The median interval between allo SCT and first dose of brentuximab vedotin was 42 months (range, 6-116).(7) Adverse events most frequently reported as being related to study drug were peripheral sensory neuropathy (n/12, 48%), nausea (n/ 7, 28%), alopecia and neutropenia (n/6, 24% each), and fatigue and vomiting (n/5, 20% each). Between transplant and brentuximab initiation 17 pts (68%) were reported to have acute/and or chronic GVHD. On brentuximab 9 pts (36%) received transient steroids for non-GVHD indications (B symptoms or infusion reactions). No GVHD was reported after initiation of brentuximab vedotin therapy.

## **2.6 CD30 expression and Graft versus Host Disease:**

CD30 expression on CD8+ T cells may be a potential biomarker for acute GVHD.(20) Chen and colleagues recently published data analyzing CD30 expression on peripheral blood T-cell subsets and soluble CD30 levels in 26 patients at the time of onset of acute GVHD (aGVHD) treatment and then compared them to transplant patients without aGVHD.(22) Analysis by flow cytometry showed that patients with aGVHD had a greater percentage of CD30 expressing CD8+ T cells with the difference especially pronounced in the central memory subset (CD30+CD8+ CD45RO+ CD62L+). Levels of central memory CD30+CD8+ CD45RO+ CD62L+ cells were 6 times higher among patients with acute GVHD than among those without aGVHD. There were similar levels of CD30 expression in naive T cells, CD4+

T cells, and regulatory (CD4+CD127lowCD25+) T cells.1(10)

Plasma levels of soluble CD30 were significantly greater in patients with GVHD and immunohistochemical analysis of affected intestinal tissue showed many CD30+ infiltrating lymphocytes present. These results suggest that CD30 expression on CD8+T-cell subsets or plasma levels of soluble CD30 may be a potential biomarker for aGVHD.

In this study we will evaluate the safety of brentuximab early after allogeneic stem cell transplant and haploidentical allogeneic transplant and observe if there is a decrease in the risk of relapse.

## 3.0 Patient Eligibility

### 3.1 Inclusion Criteria:

- 3.1.1 Patients with CD30 positive Hodgkin Lymphoma (HL) or anaplastic large cell lymphoma (ALCL) that have undergone allogeneic or haploidentical SCT in the past 60 days (matched related or matched unrelated donors only).
- 3.1.2 Age 18 to 65 years.
- 3.1.3 Performance status: Zubrod 0-1 or Karnofsky 80-100.
- 3.1.4 Serum creatinine < 1.5 mg/dL or creatinine clearance greater than or equal to 40 cc/min as defined by MDRD method from National Kidney Disease Education Program (NKDEP).
- 3.1.5 Serum direct bilirubin < 1.5 mg/dL (unless Gilbert's syndrome).
- 3.1.6 SGPT < 200 IU/L unless related to patient's malignancy.
- 3.1.7 Evidence of neutrophil and platelet engraftment, defined as platelet count equal or greater than 50,000 mm^3 independent of platelet transfusion or thrombopoietin factor and ANC equal or greater to 1000 without growth factor support for at least 5 days.
- 3.1.8 Patients with previous exposure to brentuximab pre-transplant are eligible for the study.

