### 3.2 Exclusion Criteria:

- 3.2.1 Pregnancy or breast-feeding (women of childbearing potential, any female who has experienced menarche and who has not undergone surgical sterilization or is post-menopausal with a positive serum pregnancy test).
- 3.2.2 Presence of steroid-refractory acute graft-versus-host disease (GVHD).
- 3.2.3 Patients that underwent allogeneic transplantation as a treatment of graft failure.
- 3.2.4 Dual refractory CMV reactivation to foscarnet and ganciclovir or evidence of CMV disease.

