## 4.0 Treatment Plan

### 4.1 Treatment Initiation:

Brentuximab will be given as an IV infusion over 30 minutes every 3 weeks for a total of 6 cycles. starting between days 35 and 60 post allogeneic SCT.

Brentuximab dose will be based on actual body weight starting with an initial dose of 1.2 mg/kg for the first 2 cycles and then the dose will be increased to 1.8 mg/kg after the second cycle for all subsequent cycles. Brentuximab dose will be based on actual body weight except for patients weighing more than 100 kg, then dose will be calculated based on 100 kg.

Patients must meet the following criteria to start any cycle of brentuximab:

1. Absolute neutrophil count > 1,000/mm^3 not requiring daily growth factor support on the day of the brentuximab infusion.
2. Platelet count greater than 50,000/mm^3 independent of platelet transfusions or thrombopoietin factor for at least 5 days.
3. No clinical evidence of life-threatening infection.

4. No active bleeding.
5. No uncontrolled acute GVHD (steroid refractory).
6. No CMV re-activation that is dual-refractory to foscarnet and ganciclovir/ No active CMV disease.
7. Creatinine < 1.5 mg/dL or creatinine clearance greater than or equal to 40 cc/min as defined by MDRD method from National Kidney Disease Education Program (NKDEP)
8. Serum bilirubin < 1.5 mg/dL
9. SGPT < 200 IU/L unless related to patient's malignancy

Vital sign monitoring, observation, and treatment of hypersensitivity reactions during and after infusion will be performed per standard of care.

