#### **4.3 Treatment will be discontinued if:**

1. If the dose that was administered was 1 mg/kg and the patient develops grade 4 hematological toxicity as described above.
2. If the patient develops both foscarnet and ganciclovir-resistant CMV viremia or histologic CMV end-organ disease.
3. If an anaphylactic reaction is observed.
4. If peripheral neuropathy, grade 4 is observed.
5. If progressive multifocal leukoencephalopathy (PML) is confirmed. Treatment must be withheld until PML is confirmed.
6. If the patient develops Stevens-Johnson syndrome.

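### Section 3.1.8 admits brentuximab-exposed patients unconditionally, so earlier anaphylaxis or Stevens-Johnson syndrome on the drug does not bar re-dosing, although 4.3 stops the drug for both

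*Combined protocol and SAP*

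**What the plan says.** Section 3.1.8 deals with prior treatment in one sentence: "Patients with previous exposure to brentuximab pre-transplant are eligible for the study". It does not mention tolerance or earlier toxicity.

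Section 4.3 lists six events for which treatment is discontinued. Item 3 reads "If an anaphylactic reaction is observed" and item 6 reads "If the patient develops Stevens-Johnson syndrome". Items 4 and 5 cover grade 4 peripheral neuropathy and confirmed PML. Items 1 and 2 cover grade 4 haematological toxicity at the lowest dose and treatment-resistant or end-organ CMV.

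Section 4.4 item 2 separates ordinary infusion reactions from these events: the infusion is interrupted, later infusions are premedicated, and treatment continues.

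Section 9.3 gives relapsed Hodgkin lymphoma and systemic ALCL as indications for the drug. Section 9.7.2 lists Stevens-Johnson syndrome and PML among its serious but less common reactions.

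**The concern.** The protocol treats anaphylaxis or Stevens-Johnson syndrome on study as a reason to give no more brentuximab. It applies no such rule when the same reaction to the same drug happened before the transplant. The only written rule on earlier brentuximab points towards eligibility.

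Earlier exposure is foreseeable, because the two diseases enrolled are the two for which the drug is indicated, and 3.1.8 was evidently written with that in mind. At stake is the safety of an individual patient: someone known to have reacted severely could start at 1.2 mg/kg and go on to 1.8 mg/kg from cycle 3. Neither the estimate of graft failure nor its precision is affected.

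**Working it through.** This is a check of text against text. The plan's one design figure, the 95% interval of 0 to 14.6% for a 5% graft failure rate in 20 patients (8.2), reproduces as 0.05 ± 1.96 × √(0.05 × 0.95 / 20) = 0.05 ± 0.0955. That is −4.55% to 14.55%, cut off at zero. A change to eligibility wording would not move it.

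**Step 1: every item that could keep a patient out.** The count is 8 (3.1.1 to 3.1.8) + 4 (3.2.1 to 3.2.4) + 9 (4.1 items 1 to 9) = 21.

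- 3.1: disease and transplant, age, performance status, renal function, bilirubin, SGPT, engraftment, prior exposure.
- 3.2: pregnancy or breast-feeding, steroid-refractory acute GVHD, transplant given for graft failure, and "Dual refractory CMV reactivation to foscarnet and ganciclovir or evidence of CMV disease".
- 4.1: neutrophils, platelets, infection, bleeding, GVHD, CMV, creatinine, bilirubin, SGPT.

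Items that mention earlier brentuximab: 1 (3.1.8), and it admits. Items that exclude for an earlier reaction to brentuximab: 0.

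**Step 2: 4.3 items 3 to 6 against those 21 items.**

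| 4.3 item | What could keep the patient out at entry or cycle start |
|---|---|
| 3, anaphylaxis | Nothing. A recovered patient can meet every item. |
| 6, Stevens-Johnson syndrome | Nothing. A recovered patient can meet every item. |
| 4, "If peripheral neuropathy, grade 4 is observed" | Zubrod 0-1 (3.1.3) would keep out most patients with current severe neuropathy, but not a resolved case. |
| 5, "If progressive multifocal leukoencephalopathy (PML) is confirmed" | 4.1 item 3, "No clinical evidence of life-threatening infection", would largely keep out active PML, but not a resolved case. |

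The clear gap is therefore items 3 and 6. For items 4 and 5 only a resolved event gets through.

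**Step 3: whether another provision closes the gap.**

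- 4.1 also says "Vital sign monitoring, observation, and treatment of hypersensitivity reactions during and after infusion will be performed per standard of care". This operates during and after the infusion, so after re-exposure.
- Off-study criterion 6.2 (treatment not tolerated) applies once the patient is on study.
- 4.3 itself is worded for events arising under treatment, not for history.

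None of these acts before the first study dose.

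**The case against.** The strongest reply is that eligible does not mean obliged to be treated. Section 3.1.8 says only that exposure is no bar. Harm would need an investigator to enrol, and a treating team to dose, a patient with a documented anaphylactic or Stevens-Johnson reaction to this drug. That is unlikely, and listing every such history is partly a drafting preference. This stands as to likelihood. It does not close the written gap, and the protocol does not leave CMV or GVHD to judgment: both are stated at entry and again before each cycle.

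The second reply is that no size can be given. That also stands. Purely as an assumption for scale, if all 20 patients had been exposed and 0.1% to 1% had such a history, the expected number would be 20 × 0.001 = 0.02 to 20 × 0.01 = 0.2 patients, before transplant selection and clinical judgment.

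A reader might infer more: that most of the stop events in 4.3 have no counterpart at entry. The documents do not support that as a measure of risk. The entry items that match haematological toxicity and CMV (3.1.7 and 3.2.4, with 4.1 items 1, 2 and 6) test mainly current state. If such screens count, performance status and the infection item must count in part for neuropathy and PML. Resolved PML or grade 4 neuropathy in a patient who has since had an allograft, engrafted and reached Zubrod 0-1 is remote.

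**Conclusion.** The point holds in a narrow form. As written, a patient whose earlier brentuximab caused anaphylaxis or Stevens-Johnson syndrome is eligible for re-dosing, in conflict with the protocol's own stop rule for the same events. Severity is minor. The event would be serious for the patient concerned, but is likely to be rare. No prevalence and no effect on the primary endpoint are claimed. The conclusion rests on reading 3.1.8 literally and on 4.3, 6.2 and the infusion care in 4.1 applying only once a patient is on study.

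A reader might also infer that 4.2 cannot work because 5.1 does not ask for a neuropathy grade before the first dose. The documents do not bear this out. Section 5.1 requires an examination within 5 days before that dose, 5.4 documents adverse events at about one month after transplant, and section 7.0 sets CTCAE v4.0. A stable residual grade 2 neuropathy is neither new nor worsening, so it does not meet the trigger in 4.2.

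**What to change.** Add one exclusion to 3.2: *Earlier brentuximab-related event that would require discontinuation under 4.3 items 3-6 (anaphylaxis, Stevens-Johnson syndrome; also PML or grade 4 peripheral neuropathy, for consistency).* State that earlier milder infusion reactions do not exclude, in line with 4.4 item 2.

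The cost is one line in the protocol, with no new visit or test and no change to the sample size. The downside is that, rarely, one patient is lost to accrual.

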### 3.2 Exclusion Criteria:

- 3.2.1 Pregnancy or breast-feeding (women of childbearing potential, any female who has experienced menarche and who has not undergone surgical sterilization or is post-menopausal with a positive serum pregnancy test).
- 3.2.2 Presence of steroid-refractory acute graft-versus-host disease (GVHD).
- 3.2.3 Patients that underwent allogeneic transplantation as a treatment of graft failure.
- 3.2.4 Dual refractory CMV reactivation to foscarnet and ganciclovir or evidence of CMV disease.

## 4.0 Treatment Plan

### 4.1 Treatment Initiation:

Brentuximab will be given as an IV infusion over 30 minutes every 3 weeks for a total of 6 cycles. starting between days 35 and 60 post allogeneic SCT.

Brentuximab dose will be based on actual body weight starting with an initial dose of 1.2 mg/kg for the first 2 cycles and then the dose will be increased to 1.8 mg/kg after the second cycle for all subsequent cycles. Brentuximab dose will be based on actual body weight except for patients weighing more than 100 kg, then dose will be calculated based on 100 kg.

Patients must meet the following criteria to start any cycle of brentuximab:

1. Absolute neutrophil count > 1,000/mm^3 not requiring daily growth factor support on the day of the brentuximab infusion.
2. Platelet count greater than 50,000/mm^3 independent of platelet transfusions or thrombopoietin factor for at least 5 days.
3. No clinical evidence of life-threatening infection.

4. No active bleeding.
5. No uncontrolled acute GVHD (steroid refractory).
6. No CMV re-activation that is dual-refractory to foscarnet and ganciclovir/ No active CMV disease.
7. Creatinine < 1.5 mg/dL or creatinine clearance greater than or equal to 40 cc/min as defined by MDRD method from National Kidney Disease Education Program (NKDEP)
8. Serum bilirubin < 1.5 mg/dL
9. SGPT < 200 IU/L unless related to patient's malignancy

Vital sign monitoring, observation, and treatment of hypersensitivity reactions during and after infusion will be performed per standard of care.

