#### **4.2 Dose Modification:**

Dose will be reduced from 1.8 mg/kg to 1.2 mg/kg or from 1.2 mg/kg to 1 mg/kg or from 1 mg/kg to stop treatment if:

1. Neutropenia grade 3-4 unresponsive to G-CSF or grade 4 thrombocytopenia are observed.
2. Peripheral neuropathy, new or worsening grade 2 or 3. Withhold treatment until improvement or return to grade 1 or baseline; then resume with a dose reduction.

Dose will be reduced to 1 mg/kg if:

1. Creatinine clearance < 30 cc/min as defined by MDRD method from NKDEP.  
<http://nkdep.nih.gov/lab-evaluation/qfr/estimating.shtml>
2. Hepatic impairment defined as bilirubin > 2 mg/dL.

If the patient develops grade 3-4 neutropenia unresponsive to G-CSF: Hold until resolution to grade </= 1 and restart at lower dose.

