#### **4.4 Treatment will not be dose reduced or stopped for:**

1. New onset GVHD.
2. An infusion reaction, in which case the infusion will be interrupted and appropriate medical intervention will be administered. Pre-medicate subsequent infusions with acetaminophen, an antihistamine, and/or a corticosteroid.

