## 6.0 Study Criteria

### Off Study Criteria:

- 6.1 Patient withdraws consent.
- 6.2 Patient can not tolerate treatment.
- 6.3 Unexpected pattern of toxicity.
- 6.4 Presence of both steroid and 2nd line treatment refractory GvHD while on treatment with brentuximab.
- 6.5 Presence of dual-refractory CMV reactivation to foscarnet and ganciclovir or CMV end-organ disease while on treatment with brentuximab.

- 6.6 Patient's inability of unwillingness to have follow-up visits and/or laboratory tests required by this protocol.
- 6.7 One year after treatment completion.

**Steroid refractory GVHD** is defined as: absence of any response 7 days after the initiation of corticosteroids for skin GVHD or 10-14 days after its initiation for GI and liver GVHD. Patients who are steroid refractory are not eligible to be enrolled on protocol, however if a patient develops GVHD while on protocol, brentuximab will not be held.

**Secondary graft failure** is defined as a sustained declined of ANC  $<0.5 \times 10^9/L$  for 3 consecutive days after initial documented engraftment with no evidence of disease progression and is not associated with concomitant medication that is known to cause cytopenias.

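### Once liver tests cross the Section 4.1 limits, the dosing rules for new-onset, non-steroid-refractory liver GVHD conflict, and above bilirubin 2 mg/dL they give three different instructions

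*Combined protocol and SAP*

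**What the plan says.** Four places in the protocol bear on this patient.

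- **Section 4.1** opens its list with "Patients must meet the following criteria to start any cycle of brentuximab". Item 8 reads "Serum bilirubin < 1.5 mg/dL", with no exception. Item 9 reads "SGPT < 200 IU/L unless related to patient's malignancy", so malignancy is the only exempt cause. Item 5, the GVHD condition, covers only refractory disease: "No uncontrolled acute GVHD (steroid refractory".
- **Section 4.2**, under "Dose will be reduced to 1 mg/kg if", lists "Hepatic impairment defined as bilirubin > 2 mg/dL". It does not ask about cause and has no SGPT trigger.
- **Section 4.4** begins "Treatment will not be dose reduced or stopped for", and its item 1 is new-onset GVHD, with no organ left out. It says nothing about holding or delaying a cycle.
- **Section 6**, in the note on steroid-refractory GVHD, says "if a patient develops GVHD while on protocol, brentuximab will not be held". The same note sets a response window for liver GVHD, and Section 5.3 names liver biopsy for GVHD diagnosis, so liver disease is within what the protocol means by GVHD.

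No passage says which of these takes precedence.

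**The concern.** Sections 4.1 and 4.2 act on laboratory values whatever their cause (apart from malignancy for SGPT). Section 4.4 and the Section 6 note act on the diagnosis. Liver GVHD can bring both into play together, because it can raise bilirubin or SGPT. That link is general clinical knowledge; the protocol does not state it. Section 5.2 asks for chemistries and a GVHD assessment within five days before each cycle, so the clinician would have both facts in hand at the same dosing decision.

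At stake are the dose an affected patient receives, hepatic safety, and the reading of results in patients with GVHD. Acute GVHD incidence is a secondary objective (1.2.4), soluble CD30 is to be described with and without GVHD (1.2.6), and Section 8.4 states a hypothesis linking CD30 to GVHD. If exposure among patients with GVHD varies with the reading of the protocol, those descriptions are harder to interpret. Part of the variation may also go unseen: Section 7 excludes GPT elevations from adverse events.

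**Working it through.** The plan gives no figure to reproduce. The check applies each rule, at its own threshold, to one type of patient: GVHD that is new on protocol, involves the liver and is not steroid-refractory. Such a patient passes 4.1 item 5. Off-study criterion 6.4 does not apply either, since it needs failure of both steroids and second-line treatment.

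| Laboratory state before the cycle | 4.1 items 8-9 | 4.2 bilirubin item | 4.4 item 1 | Section 6 note | Result |
|---|---|---|---|---|---|
| Bilirubin < 1.5 mg/dL and SGPT < 200 IU/L | Cycle allowed | Not triggered | No reduction or stop | No hold | No conflict |
| Bilirubin 1.5 to 2.0 mg/dL | No cycle | Not triggered | No reduction or stop | No hold | 4.1 against Section 6 |
| SGPT ≥ 200 IU/L not due to malignancy, bilirubin < 1.5 mg/dL | No cycle | Not triggered | No reduction or stop | No hold | 4.1 against Section 6 |
| Bilirubin > 2 mg/dL | No cycle | 1 mg/kg | No reduction or stop | No hold | 4.1 against Section 6; 4.2 against 4.4; 4.1 against 4.2 |

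**Spread of instructions in the last row.** Section 4.1 schedules 1.2 mg/kg for cycles 1-2 and 1.8 mg/kg afterwards. A patient on schedule could therefore be directed to:

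- no dose (4.1);
- 1 mg/kg (4.2), which is (1.2 − 1.0)/1.2 = 17% below schedule in cycles 1-2 and (1.8 − 1.0)/1.8 = 44% below it later;
- the full scheduled dose (4.4 and Section 6).

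If the patient is already at 1 mg/kg, 4.2 changes nothing and only the clash between 4.1 and the other passages remains.

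**How many patients.** The documents give no rate of liver GVHD. As an illustration only, take the 24% grade II-IV acute GVHD in the haploidentical series (Section 2.3) and the 20 patients of Section 8.2: 0.24 × 20 = 4.8 patients. With an assumed liver share of 10% to 30%, 4.8 × 0.10 = 0.5 and 4.8 × 0.30 = 1.4 patients. This is not a forecast. The series had 26 haploidentical recipients, its rate is not restricted to GVHD arising after brentuximab starts (day 35-60), and no allowance is made for liver tests that stay under the limits. In the other direction, matched-donor recipients may differ and chronic GVHD is left out. Section 2.5 reports no GVHD after brentuximab began in 25 patients, but they started a median of 42 months after transplant.

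**The case against.** The best reply is that Section 4.4 and the Section 6 note mean only that a GVHD diagnosis is not in itself a reason to act, while organ-function limits still apply. The documents lend this some support. Section 4.4 item 2 protects against stopping for an infusion reaction, yet 4.3 item 3 discontinues for anaphylaxis, so 4.4 may be a general statement that gives way to specific safety rules. The Section 6 wording cannot be absolute either, because 4.1 item 5 bars a cycle in steroid-refractory GVHD and 6.4 takes doubly refractory GVHD off study.

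The reading is plausible but not written. Where the protocol wants a cause to matter it says so: malignancy for SGPT, Gilbert's syndrome in 3.1.5. Even if accepted, it leaves 4.1 (no cycle) against 4.2 (1 mg/kg) above 2 mg/dL. A sequence of waiting until bilirubin falls below 1.5 mg/dL and then resuming at 1 mg/kg would reconcile those two, but 4.2 writes hold-then-resume for neuropathy and neutropenia and not for bilirubin. The wait would still contradict Section 6, and the lower dose would still contradict 4.4.

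Three stronger readings are tempting, and the documents do not support them.

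- A reader might infer that all non-refractory liver GVHD receives three incompatible instructions. That needs bilirubin above 2 mg/dL; raised SGPT alone never triggers 4.2.
- A reader might take 4.4 to forbid holding a cycle. It speaks of reducing and stopping; only the Section 6 note speaks of holding.
- A reader might infer damage to the main safety conclusion. The primary endpoint is secondary graft failure defined by neutrophil count, and nothing here shows an effect on it.

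**Conclusion.** The conflict is real and confined to patients whose liver tests cross the 4.1 limits: two-way at bilirubin 1.5 to 2.0 mg/dL or with SGPT alone raised, and three-way above 2 mg/dL. It rests on the rules as written, and on the premise that liver GVHD can push these tests past the limits.

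The number affected is probably small and cannot be estimated from the documents. The consequence for each such patient is direct, because the dose turns on the passage the treating clinician follows. Variation between clinicians is the relevant worry: references to the authors' own institution and standard practice (2.1, 5.4) suggest a single centre. The statistical cost is limited to hepatic safety and the description of exposure and correlative results in patients with GVHD. The point is worth correcting because it concerns dosing and the remedy is cheap, not because a main result is threatened.

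**What to change.** Reconcile 4.1 items 8 and 9, the bilirubin item in 4.2, item 1 of 4.4 and the note in Section 6. State in one place which passage governs when a bilirubin or SGPT elevation is due to GVHD, and have the other passages refer to it. The same edit should settle how 4.1 and 4.2 relate at bilirubin above 2 mg/dL, where they disagree whatever the cause. Which clinical rule to adopt is for the investigators; this review takes no position.

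The cost is one wording amendment, with no extra visits, tests or patients.
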